4.4.2 Percent change from baseline in C-reactive protein

Summary statistics (n, mean, median, SD, minimum, and maximum) and the percent change from baseline to each scheduled study assessment will be presented.

Box plots of absolute value over time and percent change from baseline to each scheduled study assessment may be presented.

A by-subject listing will also be presented.

4.4.3 Time to clinical improvement of at least 2 points (from randomization) on a 9-point category ordinal scale, live discharge from hospital, or considered fit for discharge, whichever comes first) through

This efficacy endpoint will be portrayed using the KM method. Alongside summary statistics, a KM plot of the cumulative improvement rate over time will be presented.

The HR and its 90% CI will be estimated from a Cox Proportional Hazards model (with ties = Efron), The CI calculated using a profile likelihood approach. Summary statistics will include the lower and upper quartile and median time to clinical improvement with the 90% CI.

The method for handling subjects that withdraw/ are lost to follow up or die is detailed in Section 3.3.3.

Additional sensitivity analyses may be performed as appropriate.

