1.2 Study Design

Approximately 20 participants will be included to ensure at least 16 participants are evaluable. participants will receive acalabrutinib suspension (ie, acalabrutinib 100 mg suspension in COCA-COLA® delivered via NG tube) bid for 14 days (a maximum of 28 doses). In addition to receiving best supportive care (SOC).

To assess the effect of PPIs, all participants must be receiving treatment with a PPI at the start of the study. Treatment with a PPI can begin at any time prior to enrollment, provided participants have received PPI treatment for at least 24 hours prior to the first dose of acalabrutinib suspension. Any PPI is permitted, provided it meets the minimum equivalent daily dose of 20 mg rabeprazole. Participants must be on this dosage of PPI at the start of the study. They may be weaned off PPIs during the study if medically appropriate.

[figure not shown]
Blood samples for plasma PK assessment of acalabrutinib and its metabolite (ACP-5862) will be collected at pre-dose and 0.5, 1, 2, 4, 6, and 12 hours following treatment with acalabrutinib suspension as described in the table below. Note that the sample at 12 hours must be collected prior to the subsequent acalabrutinib dose (for trough PK sample).

Table 2 PK Visit and Description

PK Visit	Description	Rationale
PK Visit 1	First PK sampling will occur on Day 1 (ie, first dosing day for acalabrutinib suspension)	Allows an early assessment of acalabrutinib and ACP-5862 PK in participants receiving acalabrutinib suspension via NG tube
PK Visit 2	Second PK sampling will occur a minimum of 4 days after the start of PPI treatment, irrespective of the timing of NG tube placement and any time after 2 doses of acalabrutinib suspension have been given (ie, PK sampling can begin prior to the third dose, or anytime thereafter) PK Visit 2 can occur as early as Day 2 (if participant has been on a PPI for ≥ 4 consecutive days prior to receiving the third acalabrutinib dose), and up to Day 4 (if participant initiated PPI treatment 24 hours prior to receiving the first dose of acalabrutinib on Day 1)	PPI exposure must occur for 4 consecutive days to reach the maximum PPI on-target effect PK sample can commence at any point after the second dose of acalabrutinib suspension to ensure steady-state levels of the active metabolite and

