1.3 Number of Subjects

Approximately 20 participants will be enrolled to have at least 16 evaluable participants. No formal power calculation is used for sample size determination. The sample size is chosen based on desire to gain adequate information while exposing as few patients as possible to the study procedure.

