4.4.1 Alive and free of respiratory failure at Day 14 (and 28)

The first efficacy endpoint is the proportion of subjects who are alive and free of respiratory failure at Day 14, where respiratory failure is defined in Section 3.3.1.

The point estimate and its 90% confidence interval (CI; using Wald method with continuity correction) will be calculated and summarized. The difference in the proportion of subjects who are alive and free of respiratory failure at Day 14 with its 90% Cis will be included in this summary. The number and percentage of subjects who experienced respiratory failure but were free of respiratory failure at Day 14 will also be included in above summary.

For those wo have respiratory failure, summary statistics for the number of respiratory failures that occurred will be summarized.

This efficacy endpoint will also be summarized (point estimate and 90% CI Wald method with continuity correction as above) by the following subgroups:

• age (predefined age categories defined in Section 4.2.3)

- sex
- race
- ethnicity
- comorbidities (present vs absent)
- history of substance abuse (former/current/never)
- Concomitant antiviral use (yes vs no)
- Respiratory failure at baseline (with vs without, defined in Section 4.2.3)

The method for handling subjects that withdraw/ are lost to follow up prior to Day 14 is detailed in Section 3.3.1.

Similar analysis will be conducted for Day 28.

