A listing of all AEs (including non-treatment-emergent events), by E-code, AE (SOC, PT, verbatim term), date of onset, date of resolution, duration, CTCAE grade, seriousness, action taken, outcome, relationship to study treatment and time from last dose to start of AE.

4.5.1.1 Deaths, serious adverse events (SAEs), and other significant adverse events The following summaries will be provided:

- A summary of the number and percentage of total deaths, deaths related to the disease under investigation (as determined by the investigator), deaths after the end of safety follow-up (28 (±3) days after last dose.
- A summary of the number and percentage of subjects reporting a treatment-emergent SAE by SOC and PT.
- A summary of the number of treatment-emergent SAEs by treatment group, SOC and PT.
- A summary of the number and percentage of subjects reporting a treatment-emergent SAE leading to discontinuation of study drug by SOC and PT.
- A summary of the number and percentage of subjects with a treatment-emergent SAE with an outcome of death by and PT.
- A summary of the primary cause of death by treatment group and PT.

Adverse events of special interest (AESI) for acalabrutinib include ventricular arrhythmias (e.g., ventricular extrasystoles, ventricular tachycardia, ventricular arrhythmia, ventricular fibrillation). AESI PTs are listed in Section 9.1. These events will be summarized as follows:

- A summary of the number and percentage of subjects reporting an AESI by CTCAE grade, group term and PT.
- A summary of the number and percentage of subjects reporting an AESI possibly related to study drug by group term and PT.
- A summary of the number and percentage of subjects reporting an AESI leading to discontinuation of study drug by SOC and PT.

A list of AESI PTs will also be provided.

Events of clinical interest (ECIs) are provided in Section 9.1. These events will be summarized similarly to AESIs and a list of ECI PTs will be provided.

The following by-subject listings will be presented:

- A by-subject listing of key information for serious adverse events (SAEs).
- A by-subject listing of key information for AESIs and ECIs.
- A by-subject listing of deaths, including the date of death, the primary and secondary cause of death, whether an autopsy was performed and whether the death was related to the disease under study.
- A by-subject listing of key information for SAEs with an outcome of death.

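### The SAP requires a difference in proportions and a Cox hazard ratio, each with a 90% CI, for a single treated group and names no comparator, reference value or covariate, so neither can be estimated as written

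*SAP*

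**What the plan says.** **Design.** Section 1.2 gives one regimen to everyone: "participants will receive acalabrutinib suspension (ie, acalabrutinib 100 mg suspension in COCA-COLA® delivered via NG tube) bid for 14 days". PPI use does not create two groups at entry either, because "all participants must be receiving treatment with a PPI at the start of the study". Section 1.3 adds that "Approximately 20 participants will be enrolled to have at least 16 evaluable participants". Table 3 in Section 2.1 defines the Efficacy Evaluable Set as everyone with at least one dose. Neither the design section nor the analysis-set section describes a control, an external reference or randomization.

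**Binary endpoint (Section 4.4.1).** The one-sample proportion with a 90% Wald interval (continuity-corrected) comes first. The section then adds: "The difference in the proportion of subjects who are alive and free of respiratory failure at Day 14 with its 90% Cis". Its last line extends the analysis to Day 28.

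**Time to improvement (Section 4.4.3).** The section specifies a KM plot, and the quartiles and median with a 90% CI. It also states: "The HR and its 90% CI will be estimated from a Cox Proportional Hazards model (with ties = Efron", with a profile-likelihood interval.

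**Related wording.** The Section 4.4.3 heading counts time from randomization, whereas Section 3.3.3 and Table 1 count it from first dose. Section 4.5.1.1 asks for "A summary of the primary cause of death by treatment group and PT". Sections 4.1 and 4.5.3 also refer to treatment groups, and the imputation table in Section 9.3 refers to a randomization date.

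**The concern.** A difference needs two proportions, and a hazard ratio needs two groups or a covariate that varies between participants. The SAP supplies neither, yet it states both outputs as things that will be produced.

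The programmer can leave them empty or choose a contrast once the data are visible. Section 4.4.1 lists eight subgroup factors, any of which could be used for that purpose. The secondary objective in Table 1 concerns adding acalabrutinib to best supportive care. A hazard ratio reported under that objective could therefore be misread as a treatment effect, which this design cannot estimate.

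**Working it through.** The SAP gives no effect size, event count or power figure to reproduce; Section 1.3 says "No formal power calculation is used for sample size determination". The check is therefore whether each quantity can be estimated.

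**1. Hazard ratio, algebra.** In a Cox model with coefficient β and covariate x, take an event time with risk set R and m tied events. The Efron contribution to the log-likelihood is β·Σx over the tied events, minus the sum over l = 0, …, m-1 of log[Σ_R exp(βx) - (l/m)·Σ_tied exp(βx)].

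If all participants share the same value x = c:
- the first term is mβc;
- each bracket equals exp(βc)·(|R| - l), so the logs sum to mβc + Σ log(|R| - l);
- the contribution is therefore -Σ log(|R| - l), and β has cancelled.

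The likelihood does not depend on β. A profile-likelihood interval keeps every β whose log-likelihood is close enough to the maximum. Here every β attains the maximum, so the interval for the hazard ratio runs from 0 to infinity.

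**2. Hazard ratio, numerical check.** The data are illustrative: 20 simulated participants, exponential times with mean 15 days rounded up to whole days, censored at Day 28, giving 18 events.

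| Covariate | β | Partial log-likelihood | Information |
|---|---|---|---|
| Constant (one group) | -2, -1, 0, 1, 2 | -41.6425 at each | 0.0 at each |
| Hypothetical two groups | -1 | -44.90 | 3.01 |
| Hypothetical two groups | 0 | -41.64 | 4.22 |
| Hypothetical two groups | 1 | -42.46 | 3.89 |

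With two groups the same 20 participants carry information. The obstacle is the missing contrast, not the small sample.

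**3. Difference in proportions.** The estimate is p1 - p2. The SAP defines p1, the proportion at Day 14 (or Day 28) in the Efficacy Evaluable Set. It defines no p2.

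**4. What remains if both are removed.** The one-sample interval is p ± [1.645·√(p(1-p)/n) + 1/(2n)]. For 10/20 the half-width is 1.645·√(0.25/20) + 0.025 = 0.184 + 0.025 = 0.209, giving 0.291 to 0.709. Illustrative counts:

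| n | Responders | 90% CI |
|---|---|---|
| 20 | 10 | 0.291 to 0.709 |
| 20 | 15 | 0.566 to 0.934 |
| 16 | 8 | 0.263 to 0.737 |
| 16 | 12 | 0.541 to 0.959 |

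The KM curve, quartiles and median also need only one group.

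**The case against.** **Could a contrast be inferred?** Three readings are possible, and the text supports none of them.
- *Subgroups.* The subgroup list follows the difference sentence and asks only for an estimate and CI within each subgroup. Section 4.4.3 names no subgroup.
- *Day 28 against Day 14.* The difference is stated at Day 14 alone, and Day 28 is a separate repeat of the analysis. A paired comparison would be conjecture.
- *An external reference.* The SAP mentions none.

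**Does it matter much?** The case for a modest rating largely stands. Table 1 makes PK and safety primary and calls the efficacy evaluation preliminary. Section 4.4 excludes p-values. No interim rule or sample-size figure uses either output. In each section the unusable item is added to a valid one-sample summary that already addresses the secondary objective. The failure would show when the program runs, so no reported number is silently biased. Section 4.1 requires departures from the SAP to be described in the study report, which lowers the risk of an undisclosed substitute. It does not say which contrast, if any, was meant.

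**Related wording.** A reader might infer that the randomization heading leaves the time origin open. It does not: Section 3.3.3 and Table 1 both fix it at first dose. A table by treatment group with one group simply has one column. These items suggest text carried over from a comparative plan, but they are not failures of estimation.

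**Conclusion.** The point holds. As written, the SAP requires two quantities that its own design cannot supply: the difference in proportions (at Day 14 and again at Day 28) and the Cox hazard ratio with its interval. With one group the information for the hazard ratio is exactly zero, whatever the sample size.

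A reader might infer that two of the three secondary efficacy analyses fail altogether, or that the trial's conclusions are at risk. The SAP does not support that. The proportions with 90% CI and the KM summaries stand, and the primary PK and safety analyses are untouched. This should be fixed, but it is a specification error in secondary descriptive outputs.

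The conclusion assumes that Sections 1.2 and 2.1 describe the whole design, with no comparator defined elsewhere. The simulated event times and responder counts are illustrative, and the conclusion does not depend on them.

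**What to change.** - **Section 4.4.1:** delete the difference-in-proportions sentence. Keep the Day 14 and Day 28 proportions with their 90% CIs.
- **Section 4.4.3:** delete the hazard-ratio and Cox sentences, including the profile-likelihood interval. Keep the KM curve, and the quartiles and median with 90% CI.
- **If a contrast was intended:** name the two groups or the reference value for the difference, and the covariate for the Cox model, before database lock. State that the result is not a treatment effect.
- **Tidy-up:** change the Section 4.4.3 heading to time from first dose, as in Section 3.3.3, and remove the treatment-group wording.

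The cost is a wording change to the SAP. It needs no new data, and deletion leaves less to program than now.

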4.5 Analysis of Safety

This section describes safety analyses to be conducted. All of the analyses in this section will be based on the safety population and will be performed for all safety variables specified below. All analyses of safety data will employ descriptive statistics.

4.5.1 Adverse events

Verbatim descriptions of AEs will be mapped per version 23.0 of the MedDRA thesaurus terms and graded per National Cancer Institute (NCI) CTCAE, v5.0 or higher. Unless stated otherwise, only treatment-emergent adverse events (TEAEs) (TEAEs are AEs starting or ongoing AEs worsening after the first dose of study treatment and AEs with start date up to the last dose of study treatment plus 28 (±3) days) will be presented in the summaries. When programmatically assigning the AEs as treatment emergent, the upper window will be used.

The following summaries will be provided:

- A summary of the number and percentage of subjects reporting any TEAE, TEAEs with outcome of death, at least one TEAE of CTCAE grade 3 or higher, at least one serious TEAE, at least one TEAE possibly related to study drug, and at least one TEAE leading to discontinuation of study drug.
- A summary of the number of TEAEs, TEAEs with outcome of deaths, TEAEs with CTCAE grade 3 or higher, serious TEAEs, TEAEs possibly related to study drug, and TEAEs leading to discontinuation of study drug.
- A summary of the number and percentage of subjects reporting a TEAE by SOC and PT.
- A summary of the number and percentage of subjects reporting the most common TEAEs (occurring in at least 5% of overall subjects) by SOC and PT.
- A summary of the number and percentage of subjects reporting a TEAE by CTCAE grade, SOC and PT.
- A summary of the number and percentage of subjects reporting a TEAE with CTCAE grade 3 or higher by SOC and PT.
- A summary of the number and percentage of subjects reporting a TEAE possibly related to study drug by SOC and PT.
- A summary of the number and percentage of subjects reporting a TEAE leading to discontinuation of study drug by SOC and PT.

For the most common TEAEs, all events that occur in at least 5% of subjects overall will be summarized by preferred term, by decreasing frequency. This cut-off may be modified after review of the data. When applying a cut-off (e.g., 5%), the raw percentage should be

compared to the cut-off, no rounding should be applied first (i.e., an AE with frequency 4.9% will not appear if the cut-off is 5%).

The following by-subject listings will be provided:

A listing of all AEs (including non-treatment-emergent events), by E-code, AE (SOC, PT, verbatim term), date of onset, date of resolution, duration, CTCAE grade, seriousness, action taken, outcome, relationship to study treatment and time from last dose to start of AE.

4.5.1.1 Deaths, serious adverse events (SAEs), and other significant adverse events The following summaries will be provided:

- A summary of the number and percentage of total deaths, deaths related to the disease under investigation (as determined by the investigator), deaths after the end of safety follow-up (28 (±3) days after last dose.
- A summary of the number and percentage of subjects reporting a treatment-emergent SAE by SOC and PT.
- A summary of the number of treatment-emergent SAEs by treatment group, SOC and PT.
- A summary of the number and percentage of subjects reporting a treatment-emergent SAE leading to discontinuation of study drug by SOC and PT.
- A summary of the number and percentage of subjects with a treatment-emergent SAE with an outcome of death by and PT.
- A summary of the primary cause of death by treatment group and PT.

Adverse events of special interest (AESI) for acalabrutinib include ventricular arrhythmias (e.g., ventricular extrasystoles, ventricular tachycardia, ventricular arrhythmia, ventricular fibrillation). AESI PTs are listed in Section 9.1. These events will be summarized as follows:

- A summary of the number and percentage of subjects reporting an AESI by CTCAE grade, group term and PT.
- A summary of the number and percentage of subjects reporting an AESI possibly related to study drug by group term and PT.
- A summary of the number and percentage of subjects reporting an AESI leading to discontinuation of study drug by SOC and PT.

A list of AESI PTs will also be provided.

Events of clinical interest (ECIs) are provided in Section 9.1. These events will be summarized similarly to AESIs and a list of ECI PTs will be provided.

The following by-subject listings will be presented:

- A by-subject listing of key information for serious adverse events (SAEs).
- A by-subject listing of key information for AESIs and ECIs.
- A by-subject listing of deaths, including the date of death, the primary and secondary cause of death, whether an autopsy was performed and whether the death was related to the disease under study.
- A by-subject listing of key information for SAEs with an outcome of death.
- A by-subject listing of key information for AEs leading to discontinuation of study treatment.

The following subject narratives will be provided:

- Narratives of SAEs with an outcome of death.
- Narratives of SAEs with an outcome other than death.
- Narratives of discontinuation of investigational product due to AEs.
- Narratives of AESIs.
- Narratives of any other medically-relevant AE that does not fall into the above categories.

4.5.2 Exposure, dose intensity and treatment compliance

Study drug exposure will be listed and summarized for acalabrutinib-treated subjects in the SAF. The following summaries will be produced using the definition of exposure variables in Table 5 in Section 3.2.3:

- Intended treatment duration
- Actual treatment duration
- Summary statistics (n, mean, median, SD, minimum, and maximum) of RDI
- The number and percentage of dose interruptions, dose increases, and reasons for dose interruptions and dose increases
- Calculated average daily dose
- Treatment compliance

4.5.3 Laboratory assessments

For the following continuous laboratory parameters, summary statistics (n, mean, median, SD, minimum, and maximum) of the laboratory results (conventional units and System

International (SI) units) and the change from baseline at each scheduled post-baseline assessment will be presented:

- Fibrinogen
- PT
- aPTT
- INR
- D-dimer
- CRP
- Procalcitonin
- Cardiac troponin
- BNP

Selected laboratory parameters (including categorical parameters) may be analysed with shift tables (defined by the normal ranges) of baseline to minimum post-baseline value (low, medium, high) and of baseline to maximum post-baseline value (low, normal, high) may be presented. For laboratory parameters classified using CTC grades, shift tables for selected laboratory parameters may also be produced showing baseline CTC grade to maximum post-baseline CTC grade by treatment group.

By-subject listings of haematology and clinical chemistry parameters will be presented. Unscheduled laboratory results will not be included in the by-visit summaries but will be included in any out of range or shift tables of worst postbaseline data.

Liver function abnormality by Hy's law and frequencies of abnormal treatment emergent uric acid will be summarized.

4.5.4 Vital signs

Summary statistics (n, mean, median, SD, minimum, and maximum) for each of the vital signs and the change from baseline at each scheduled post-baseline assessment will be presented.

A by-subject listing of all vital sign parameters will be presented; abnormal vital signs will be flagged.

4.5.5 Physical examinations and chest imaging, electrocardiograms and echocardiograms

By-subject listings of all physical examination and weight data will be presented.

By-subject listings of chest imaging (when clinically indicated) findings will be presented.

If there is a sufficient number of subjects with post-baseline assessments (≥10 subjects), a shift table of the number and percentage of subjects with normal or abnormal ECG evaluations may be presented from baseline to the most extreme post-baseline evaluation.

By-subject listings of all ECG parameters will be presented along with the heart rhythm and overall evaluation of ECGs at all visits.

By-subject listings of ECHO overall evaluation, abnormalities and LVEF will be presented.

